4.1. Protocol Deviations

- Important protocol deviations (including deviations related to study inclusion/ exclusion criteria, conduct of the trial, patient management or patient assessment) will be summarised and listed. Note, only important protocol deviations that occurred during BEL114333 will be reported.
- Protocol deviations will be tracked by the study team throughout the conduct of the study in accordance with the Protocol Deviation Management Plan Version 3 (dated: June 21, 2017).
 - Data will be reviewed prior to freezing the database to ensure all important deviations are captured and categorised on the protocol deviations dataset.
 - This dataset will be the basis for the summaries and listings of protocol deviations.
- A separate summary and listing of all inclusion/exclusion criteria deviations for BEL114333 will also be provided. This summary will be based on data as recorded on the inclusion/exclusion page of the eCRF.

5. CONSIDERATIONS FOR DATA ANALYSES AND DATA HANDLING CONVENTIONS

Table 2 provides an overview of appendices within the RAP for outlining general considerations for data analyses and data handling conventions.

Table 2 Overview of Appendices

Section	Component
11.1	Appendix 1: Time & Events Section 11.1.1: BEL114333 Protocol Defined Time & Events
	Section 11.1.2: Parent Study Protocol Defined Time & Events
11.2	Appendix 2: Assessment Windows Section 11.2.1: Year Intervals
	Section 11.2.2: Belimumab Visits
11.3	Appendix 3: Adverse Event Collapsing Rules and Assignment of Adverse Events to Study Year
	Section 11.3.1: Adverse Event Collapsing
	Section 11.3.2: Assigning Adverse Events to Study Year
11.4	Appendix 4: Data Display Standards & Handling Conventions
	Section 11.4.1: Study Treatment & Sub-group Display Descriptors
44.5	Section 11.4.2: Baseline Definition
11.5	Appendix 5: Derived and Transformed Data
	Section 11.5.1: General Section 11.5.2: Study Population
	Section 11.5.3: Safety
	Section 11.5.4: Efficacy
	Section 11.5.5: Biomarkers
11.6	Appendix 6: Premature Withdrawals & Handling of Missing Data
	Section 11.6.1: Premature Withdrawals and Completion
	Section 11.6.2: Handling of Missing Data
11.7	Appendix 7: Methods for Handling Centres
11.8	Appendix 8: Examination of Covariates, Subgroups & Other Strata
	Section 11.8.1: Handling of Other Strata and Covariates
	Section 11.8.2: Handling of Subgroups
11.9	Appendix 9: Laboratory Parameters & Adverse Events Grading Tables
	Section 11.9.1: Laboratory Parameters
	Section 11.9.2: Adverse Event and Laboratory Value Severity Grade Tables
11.10	Appendix 10: PSAP Sections for AESI Reporting.

5.1. General Data Considerations

- This is a multi-centre study in Japan and Korea. There are no planned adjustments made for multiple centres or regions.
- As no formal hypotheses are being tested, there are no planned adjustments for multiple comparisons or multiplicity.
- As all subjects will be treated with belimumab and there are no hypothesis tests, no additional strata or covariates will be employed in the analyses. Subgroups will be defined for further exploration of the data in a descriptive fashion.
- Reporting of data is by year of belimumab treatment beginning on the date when subjects received their first dose of belimumab, irrespective of the formulation (Section 2.4.1 and Section 11.2.1).
- Baseline is defined as the last available value prior to the initiation of treatment with belimumab and will henceforth be referred to as 'Belimumab baseline'. See Appendix 4: Data Display Standards & Handling Conventions for more details on baseline definitions.
- For summaries performed by belimumab visit, placebo subjects are aligned based on start of exposure to belimumab (see Section 11.2.2 for details of the visit mapping).
 - Note, for BEL114333, subjects randomized to belimumab in the parent study were off-set by an additional 4 weeks compared to the open-label visit schedule, in order to complete the final assessments at the parent study Week 52 visit. Therefore, the mapping was adjusted in order to align the ensuing open-label visits. This was achieved by mapping the parent study Week 52 visit to the Belimumab Visit Year 1 Week 48 (and dropping the parent study Week 48). Ongoing open-label visits will always align.

Note, for subjects ongoing in BEL114333 at the time of study end, there is one year off-set between the parent randomised treatment groups until the last dose was administered in March 2018. Data for the last year will be limited to the belimumab group.

• There is a single data base that captures both parent study (i.e. DB phase of BEL113750) and open-label data for study BEL113750. The dividing line between parent study and open-label data is determined by the Day 365 visit. Any new data after this visit is regarded as open-label.

Note, after the database was frozen for the parent study analysis (DB data), technical limitations required the entire data base to be open in order to enter open-label information. Thus, sites had the ability to also change data pertaining to the parent study.

• A complete BEL113750 database extraction will be performed (because the DB data will be used in the open-label analyses). Note, there are differences between the prior DB data extraction by a different vendor/format and the open-label data. The complete extraction will enable all the data to be compatible.

The complete extraction will be able to include any additional parent study information (e.g., SAEs, concomitant meds) entered by sites at any time from the start of the parent study, and will be included in aggregate reporting.
 Note any additional SAEs will also be mentioned separately in the open-label phase CSR.

The same database captures data for BEL114333. Similarly, the BEL114333 sites had the ability to also change data pertaining to the parent study BEL113750, per the above

- From the complete database, a selected data extraction of the BEL114333 data will be performed
- The DB data for Japan and Korea subjects will be extracted from the complete BEL113750 data (previously used for the BEL113750 China OL analysis).

Lastly, the BEL112341 Japan subjects who entered BEL114333 will have all relevant data extracted from the complete BEL112341 database.

All relevant belimumab data from the parent studies and study BEL114333 will be aggregated.

Unless otherwise stated, the following statistics will be used to summarise the data:

- Continuous Variables: n, mean, standard deviation (SD), median, 25th & 75th percentiles, minimum and maximum.
- Categorical Variables: n, frequency counts and percentages.

Unless otherwise stated, the following rules will be implemented:

- Summaries by Visit: Only scheduled visits will be presented (i.e. that correspond to the timings of the open-label visits for BEL114333). Otherwise data not shown here will be displayed in listings, and used in derivations such as "any time post-baseline" summaries for laboratory data, time to event, etc. Exit visits will be slotted to the next 6 monthly scheduled visit for that year for efficacy endpoints (or next 12 monthly scheduled visit for SLICC). Otherwise, data will be summarised per the nominal visit.
- Due to the additional 6 month OL extension for SC subjects entering BEL114333, there is a 6 month off-set in the data capture between the parent studies. As a result, for SLICC, immunoglobulins and B cell subsets, captured on an annual basis in BEL114333, the data captured at each analysis visit stratifies by parent study. As such these endpoints will be tabulated by parent study, and the data will not be aggregated.
- Summaries by belimumab Treatment: Data will be mapped to the year by windowing starting at the time of first belimumab treatment.

The GlaxoSmithKline group of companies

BEL114333

- Listings: If endpoints reported, data will be presented in listings as required.
- Figures: error bars will be displayed.

Unless otherwise stated, no imputation for missing values will be conducted.

6. STUDY POPULATION ANALYSES

The study population analyses will be based on the Safety population, unless otherwise specified.

6.1. Overview of Planned Analyses

Table 3 provides an overview of the planned study population analyses, with full details of data displays being presented in Appendix 12: List of Data Displays.

Table 3 Overview of Planned Study Population Analyses

Display Type	Data	Data Displays Generated		
	Table	Figure	Listing	
Subject Disposition				
Subject Enrolment (All Subjects Population)	Y [1] [2]			
Enrolment by Site	Y [1]			
Belimumab Treated Subject-Years on Study	Y [3]			
Subject Disposition (All Enrolled Subjects Population)	Y [4]			
Reasons for Study Withdrawal			Y [5]	
Study Completion Status per Protocol	Υ [6]		Y [7]	
Time to Withdrawal Prior to Study Closing	Υ [8]	Y [8]		
Subject Completion Status per Protocol by Year Interval	Υ [9]			
Inclusion/Exclusion Criteria				
Inclusion/Exclusion Criteria Deviations	Y [1]		Υ	
(All Enrolled Subjects Population)	1 1.1		ĭ	
Protocol Deviations				
Subjects with Important Protocol Deviations	Y [1]		Υ	
(All Enrolled Subjects Population)		Ţ		

NOTES:

- T = tables, F = Figures, L = Listings, Y = Yes display generated.
- [1] Summarised by parent randomised treatment group and the total population.
- [2] Summarises No. (%) of Japan and Korea subjects randomised & completed parent study BEL113750, and those subjects who were enrolled and included in the Safety population for BEL114333. Additionally, Japan subjects from BEL112341 are also summarised.
- [3] Summarises person-years and cumulative person-years for time on belimumab treatment by year interval and parent randomised treatment group, and person-years for at any time post-baseline up to a subject's final contact. See Section 11.5.1 for definition of final contact.
- [4] Summarises subject disposition per End of Treatment CRF page as determined by the investigator. Note, the CRF page does not include an option for selecting study completion. Thus, all subjects were indicated as being withdrawn.
- [5] Listing indicates reasons and time of withdrawal per End of Treatment CRF page (see footnote 4).
- [6] Summarises study completion status per protocol (completed, death, withdrawn [and reasons for withdrawal]). See Section 11.6.1 for definition of study completion.
- [7] Listing indicates subject completion status (see footnote 6) and whether subjects are included in analysis populations.
- [8] Kaplan-Meier plot of time (in days) to withdrawal (see footnote 6 for definition of withdrawal) and associated summary table. See Section 11.5.1 for derivation of time to withdrawal. Note: subjects who died or completed the study per the protocol, will be censored.
- [9] Summarises No. (%) of subjects starting each year interval, and of those, the number completed, died and withdrawn [and reason for withdrawal], or ongoing in the study at the end of that year interval. Will be summarised using frequencies and percent. The denominator for each year will be the number of subjects who started each year of treatment.

6.2. Overview of Planned Demography & Baseline Characteristics Analyses

Table 4 provides an overview of the planned demography and baseline characteristics analyses, with full details of data displays being presented in Appendix 12: List of Data Display.

Table 4 Overview of Planned Demography & Baseline Characteristics & Medical History Analyses

Display Type	Data Display'	s Generated
	Table	Listing
Demography & Baseline (BL) Characteristics		
Demographics & BL Characteristics	Υ	Y (x6) [3]
Demographics & BL Characteristics by Age Group (< 65 vs ≥ 65 years)	Y (x2) [1]	
Demographics & BL Characteristics by Sex (Male vs Female)	Y (x2) [1]	
Demographics & BL Characteristics by BL SELENA SLEDAI (≤ 9 vs ≥ 10)	Y (x2) [1]	
Summary of Age Ranges (All Enrolled Subjects Population)	Y	
Race and Racial Combination Details (All Enrolled Subjects Population)	Υ	Υ
Medical History		
Medical History		Y [4]
Baseline Disease Activity		
Baseline Disease Activity	Υ	
Baseline Disease Activity by Age Group (< 65 vs ≥ 65 years)	Y (x2) [1]	
Baseline Disease Activity by Sex (Male vs Female) Y (x2)		
Baseline Disease Activity by BL SELENA SLEDAI (≤ 9 vs ≥ 10)	Y (x2) [1]	
Other Baseline		
Allowable SLE Medication Usage at Baseline	Υ	
ACR Classification Criteria at Parent Study Baseline	Υ	
SELENA SLEDAI Organ & Item Involvement at Baseline Y		
BILAG Grade by Organ Domain at Baseline Y		
Complement Levels at Baseline	Υ	
Autoantibody Levels at Baseline	Y	
Immunoglobulin Levels at Baseline	Y [2]	
B Cells at Baseline (Japan Only)	Υ	

NOTES:

- BL= Baseline, T = Tables, L = Listings, Y = Display Generated, (xN) = Number of separate displays generated
- [1] Separate displays generated for each sub-group level.
- [2] Parameters summarised: IgG, IgM and IgA.
- [3] Separate listings generated for [A] Demographic Characteristics [B] Anti-dsDNA, ANA, Complement Levels and SLE Medication Use [C] Disease Duration, PGA, SLICC/ACR Damage Index and Proteinuria Results [D] SELENA SLEDAI Results [E] BILAG Index Results [F] SLE Flare Index.
- [4] Medical history data were collected at screening of the parent studies. The baseline definitions for the parent randomised treatment groups are different for the open-label analysis. See Figure 1. Thus, for subjects who were randomised to placebo in the parent study, any AEs with end dates prior to the first open-label belimumab dose (i.e. either in BEL112341 open-label extension or BEL114333), will be included as medical history terms. For subjects who were randomised to belimumab in the parent study, any AEs that started before the first belimumab dose in the parent study, will be included as medical history terms; any AEs that started on or after the first belimumab dose with end dates during the parent study will be summarised as AEs.

6.2.1. Demography

Baseline measurements for subjects are defined in Section 11.4.2. Data presentations will be summarized by parent randomized treatment group and overall.

Descriptive statistics will be used to summarize the continuous demographic and baseline characteristics of age at start of belimumab treatment (years), height (cm), weight (kg), BMI (kg/m²).

Counts (%) of the following categorical demographic and baseline characteristics will be presented: sex, race, race category, ethnicity.

The summary of demographic and baseline characteristics will be repeated for subgroups, where the subgroup categories are defined in Appendix 8: Examination of Covariates, Subgroups & Other Strata.

6.2.1.1. Baseline Disease Characteristics

A summary of baseline disease activity will be provided, including counts and percentages for categorical endpoints defined in Table 5.

Descriptive statistics for the continuous scores will be presented for SELENA-SLEDAI, PGA and SLICC/ACR Damage Index. The summary of baseline disease activity will be repeated for subgroups. Refer to Appendix 8: Examination of Covariates, Subgroups & Other Strata.

 Table 5
 Baseline Disease Endpoints

Endpoint	Categories
BILAG Organ Domain Involvement	At least 1A or 2B, At least 1A, At least 1B, No A or B [1]
SELENA-SLEDAI	≤ 9 or ≥ 10
SLE Flare Index	No flare, At least 1 flare, At least 1 severe flare [2]
PGA	0 to 1, >1 to 2.5 or > 2.5
SLICC/ACR Damage Index	0, 1 or >1
Baseline Proteinuria (measured by spot	≤ 0.5 or > 0.5
urine protein creatinine ratio mg/mg)	Subcategories of > 0.5 mg/mg: >0.5 to < 1, 1 to < 2 or ≥ 2

NOTES:

- [1] "No A or B" is to mean "Neither A nor B", equivalently, "No A and No B", and not "No A or No B". A footnote should be added to the SAS output.
- [2] See Section 11.4.2.3 for derivation of flare categories.

Table 6 provides indicators of baseline disease activity that will also be summarized.

Table 6 Baseline Indicators of Disease Activity

Baseline Indicator	Categories & Summaries at Baseline
SLE Disease Duration (yrs)	Summary statistics
ACR Classification Criteria	Count (%) with each symptom present and total at baseline, and total number of ACR criteria met. NOTE: ACR classification is collected at screening of the respective parent studies, and therefore based on parent study screening assessment.
SELENA-SLEDAI category	Count (%) for each organ domain and item present.
BILAG	Count (%) of each A – E score by organ domain.
Autoantibody Levels (anti-dsDNA, ANA)	 Count (%) for negative and positive (Anti-ds DNA: ≥ 30 IU/ml & ANA ≥ 0.80 Index [BEL113750] or ANA ≥ 80 Titer [BEL112341]) Summary statistics for positive Anti-dsDNA and positive
0 1 1 (00 01)	ANA.
Complement Levels (C3, C4)	Summary Statistics. I am Narmal and High C2
	 Low, Normal, and High C3 C3 count (%) of low (< 90 mg/dL), normal, and high (> 180 mg/dL)
	Low, Normal, and High C4
	 C4 count (%) of low (< 10 mg/dL), normal, and high (> 40 mg/dL).
Immunoglobulin Levels (IgG, IgA, and	Summary statistics.
IgM [g/L])	 Count (%) below the lower limit of normal (LLN) and above upper limit of normal (ULN). See Section 11.5.5 for definitions.
Allowable SLE Medication Usage	Counts (%) by class for: Steroid only, Immunosuppressant only, Anti-malarial only, Steroid and Immunosuppressant only, Steroid and Anti-malarial only, Immunosuppressant and Anti-malarial only, Steroid, Immunosuppressant and Anti-malarial only.
	Counts (%) for preferred term within drug class (Steroid, Other Immunosuppressant/immunomodulatory Agents, Anti-malarial, NSAIDs and Aspirin).
Average daily prednisone dose (mg/day)	Summary statistics.
at baseline	• Counts (%) for dose categories: 0, >0 to ≤ 7.5, >7.5 to ≤ 40 and >40 mg/day

7. SAFETY ANALYSES

The safety analyses will be based on the Safety population, unless otherwise specified.

7.1. Overview of Planned Medications and Exposure Analyses

Table 7 provides an overview of the planned analyses of medications and exposure, with full details of data displays being presented in Appendix 12: List of Data Displays.

Table 7 Overview of Planned Medications & Exposure

Display Type		Absolute	
	Sum	Summary	
	Т	F	L
Medications			
Concomitant Medications by ATC Level 1 & ATC Level 4 Term	Υ		Υ [1]
Concomitant Medications by ATC Level 4 & Preferred Term	Υ		Υ [1]
Concomitant Procedures/Surgery			Υ
SLE Medication Use by Year Interval	Υ		
Prednisone and Other Corticosteroids by Year Interval	Υ [2]		
Prednisone Dose Shifts from BL by Visit	Υ		Υ
Exposure			
Study Drug Exposure	Υ		Υ
Study Drug Administration			Υ

NOTES:

- BL = Baseline, T = Table, F = Figure, L = Listing, Y = Yes display generated, (xN) = number of separate displays generated.
- Summary = Represents TFL related to any summaries (i.e. descriptive statistics) of the observed raw data.
- Individual = Represent L related to any displays of individual subjects observed raw data.
- [1] Listing by ATC code 1 and 4, Preferred and verbatim term.
- [2] Maximum Daily Prednisone Equivalent Corticosteroid Daily Dose Category

7.1.1. Concomitant Medications

- Concomitant medications are defined as medications that started on or before the first dose of belimumab treatment, which continued during the belimumab treatment period, or medications that started after the first belimumab dose. See Section 11.6.2 for details of handling missing and partial dates.
- Summaries will be performed by the parent randomised treatment group and the total Safety population.
- Concomitant medications in BEL114333 will be coded and reported based on the
 current version of the GSK Drug Dictionary (version 1.6) at the time of study
 reporting (study BEL114333). To comply with fulfilling any PMDA regulations, the
 concomitant medications will also be coded using the WHO-DRUG dictionary.
 Outputs using the WHO-DRUG dictionary will be produced on request.

NOTE: the same version of the GSK Drug Dictionary which was used at the time of reporting the parent studies will be used for this current reporting (BEL113750, version 1.4; BEL112341, version 1.3). Any major coding discrepancies between different versions of GSK Drug can be addressed in a CSR appendix, if necessary.

O WHO coded medications will not be provided for BEL112341 because the BEL112341 reporting predates the PMDA regulations requiring WHO coded data. The BEL112341 data were only coded using GSK DRUG at the time of reporting (CSR effective date 26 Sep 2016). WHO coded medications will be provided for BEL113750.

Note: medications which do not have pharmacological properties are not coded to ATC descriptions, and therefore, will be assigned programmatically to an ATC Level 1 term of "PHARMACOLOGICAL PROPERTIES CANNOT BE REFERENCED". These medications are identified by a blank ATC Level 1 term (CMATC1).

For summaries performed by ATC Level 4, medications that have no ATC Level 4 term, will be summarised according to the lowest ATC level categorisation based on the level of specificity of the medication therapeutic action.

• Listings of concomitant medications will be presented.

7.1.1.1. Concomitant Medication Collapsing Rules

- Concomitant medications were collected in both the parent studies and study BEL114333.
- Due to the ongoing nature of some concomitant medications at the end of the parent study, some medications occur in both the parent study and study BEL114333.
- The following table shows where medications reside by their relationship to the parent study exit date or Year 1 Day 0 visit of the BEL114333 study.

Medication Occurrence	Database
CM starts and ends on/before parent study Exit Visit.	Parent study only
CM starts on/before Exit Visit in the parent study and ends either on/after Year 1 Day 0 of BEL114333, or after the Exit Visit but before Year 1 Day 0 of BEL114333 (where there is a gap between these visits). ¹	Parent study and BEL114333 ²
CM starts after Exit Visit of the parent study and ends before Year 1 Day 0 of BEL114333 (where there is a gap between these visits).	BEL114333 only
CM starts after Exit Visit of the parent study and ends on/after Year 1 Day 0 of BEL114333 (where there is a gap between these visits).	BEL114333 only
CM starts and ends on/after Year 1 Day 0 of BEL114333.	BEL114333 only

- Medications that occur in both the parent study and BEL114333 will be collapsed based on the following dataset attributes: GSK Drug Preferred Term, medication start date, dose, unit, frequency, route and reason/indication.
 - Medication end date should reflect the final date in BEL114333, as appropriate.

7.1.2. SLE Medications

- Corticosteroids, anti-malarials, other immunosuppressive/immunomodulatory agents, NSAIDs and Aspirin will be categorized based on the coded preferred terms, and summarized by yearly interval using frequencies (%).
- For summaries, all corticosteroids taken during belimumab treatment are converted to a prednisone equivalent dose (mg/day). This then can be used for the derivation of average daily dose, see Appendix 5: Derived and Transformed Data.
- Use of prednisone or other corticosteroids during the study were collected as a running log with other concomitant medications, and will be summarized using dose level categories: 0, > 0 to ≤ 7.5 or > 7.5 to ≤ 40 , and > 40 mg/day.

7.1.3. Maximum Daily Prednisone Equivalent Corticosteroid Daily Dose Category

Prednisone equivalent corticosteroid daily dose will be mapped to belimumab visits occurring at Year 1 Day 0, as well as weeks 24 and 48 for each year per the definitions in Appendix 5: Derived and Transformed Data.

Maximum prednisone equivalent corticosteroid daily dose will be summarised within the year intervals.

Categories reported as

[1] No prednisone use (0 mg prednisone equivalent)

[2] > 0 to ≤ 7.5 mg prednisone equivalent

[3] > 7.5 to ≤ 40 mg prednisone equivalent

[4] > 40 mg prednisone equivalent

[5] Unknown

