11.1. Appendix 1: Time & Events

11.1.1. BEL114333 Protocol Defined Time & Events

11.1.1.1. Open-label Year 1

Study Visit	Wk 48 of BEL 113750/ On/before Day 168 of C11151	Wk 0 (Wk 52 of BEL11375 0/Day 168 of C1115) +1 week ¹	Wk 4	Wk 8	Wk 12	Wk 16	Wk 20	Wk 24	Wk 28	Wk 32	Wk 36	Wk 40	Wk 44	Wk 48	EXIT ²	16 wk FU ± 7d post infusion	6 month FU ± 7d post infusion
Study Day		Day 0	28 ±7d	56 ±7d	84 ±7d	112 ± 7d	140 ±7d	168 ±7d	196 ±7d	224 ±7d	252 ±7d	280 ±7d	308 ±7d	336 ±7d			
Written Informed Consent	Х																
Inclusion/Exclusion Criteria		X*															
Efficacy Assessments																	
Disease Activity Scales: SELENA SLEDAI, SLE Flare Index, BILAG and PGA ³		Х						x						Х	х		
SLICC/ACR Damage Index		Х												Х	Х		
Safety Assessments																	
Symptom-driven Physical Exam		X						Х						Х	Х	Х	
Record Concurrent Medications		Х	Х	Х	Х	Х	Х	Х	Χ	Х	Х	Х	Х	Х	Х	Х	
Assess/Record Adverse Events ⁴		Х	Х	Х	Х	Х	Х	Х	Χ	Х	Х	Х	Χ	Х	Х	Х	
Vital Signs 5, 11		Χ	Χ	Χ	Χ	Χ	Χ	Χ	Χ	Χ	Χ	Χ	Χ	Χ	Χ	Х	

Study Visit	Wk 48 of BEL 113750/ On/before Day 168 of C11151	Wk 0 (Wk 52 of BEL11375 0/Day 168 of C1115) +1 week ¹ Day 0	Wk 4	Wk 8	Wk 12	Wk 16	Wk 20	Wk 24	Wk 28	Wk 32	Wk 36	Wk 40	Wk 44	Wk 48	EXIT ²	16 wk FU ± 7d post infusion	6 month FU ± 7d post infusion
Study Day			±7d	±7d	±7d	$\pm 7d$	±7d										
Laboratory Assessments																	
Labs: Haematology & Modified Chem 20 (non fasting) ⁵		Х	Х		х			Х			х			Х	Х	Х	
Urinalysis ⁵		Х	Χ		Χ			Χ			Χ			Х	Х	Χ	
Spot urine (protein to creatinine ratio) ^{5, 6}		Х						Х						Х	Х		
Urine Pregnancy Test 5,7		Х	Х	Х	Х	Х	Х	Х	Х	Х	Х	Χ	Χ	Х	Х	Х	
C3, C4, Anti-ds DNA Autoantibodies ⁵		Х						Х						Х	Х		
IgG ^{5, 8}		Х			Χ			Χ						Х	Х	Х	
IgA & IgM ^{5, 8}		Х												Х	Х		
PT/ PTT		X*															
Exploratory Lab Assessments																	
Immunogenicity 9		Х						Χ						Х	Х	Χ	X ^{9A}
B cell Markers 10		Χ												Х	Х		Χ
Investigational Product																	
Belimumab Administration 11, 12		Х*	Х	Х	Χ	Х	Х	Х	Х	Х	Х	Х	Х	Х			

Calendar represents a yearly (48-week) ongoing visit schedule until the subject is terminated from the study. During the first 48 weeks, the 1st visit is Baseline/Day 0. For all subsequent 48 week calendar years, the 1st visit will be Week 4. Note: BEL112341 is referred to as 'C1115' in this time and events table.

*See footnote 1.

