11.2.1. Year Intervals

- To report subject disposition and AE assessments with similar durations of exposure to active belimumab treatment, assessments will be slotted into year intervals using a 365-day calendar year.
- Few subjects are expected to have > 6 years exposure and therefore "Year 6+" will be extended to the last available visit.
- For subjects who withdraw during an interval, the end date of their final interval will be set to their exit visit date.
- For summaries, the "Any Time Post-Baseline" includes the follow-up visits, where follow-up visits are excluded from the "Year 6+" year interval.
- For laboratory assessments, the worst value/highest toxicity reported over the year
 interval will be used in the analyses. Concomitant medications will be reported by
 what medications a subject is taking during the interval. In addition, AEs will be
 reported by start date. Subject disposition, worst value/highest toxicity laboratory
 assessments, concomitant medications, and AEs will be summarized according to the
 following year categories.

Study Year	Belimumal	o Study Days
	Start Day	End Day
Year 0-1	Day 1 ^[1] First Treatment Date	Day 365
Year 1-2	Day 366	Day 730
Year 2-3	Day 731	Day 1095
Year 3-4	Day 1096	Day 1460
Year 4-5	Day 1461	Day 1825
Year 5-6	Day 1826	Day 2190
Year 6+	Day 2191	Maximum Study Day [2]

NOTES:

- [1] Protocols specify Day 0 as First Treatment, but due to CDISC standard implementation first treatment date will appear as Day 1 in the analyses. Also, first treatment date refers to first belimumab treatment, regardless of originally randomized treatment.
- [2] Last visit date will be defined as the exit visit date where applicable. Subjects who do not have an exit visit date and only a follow up date, the date of the follow up will be used. See Section 11.5.1 for more details.

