- Concomitant medications, including corticosteroids, were collected in both the parent studies and BEL114333. To determine average daily dose and for analysis of steroid use, all steroid dosages are converted to a prednisone equivalent dosage in milligrams.
- The average daily prednisone dose considers all steroids taken systemically intravenously (IV), intramuscularly (IM), SC, intradermally, and orally for both SLE and non-SLE reasons.
- At baseline, the average daily prednisone dose is the sum of all prednisone doses over 7 consecutive days up to, but not including Day 0, divided by 7.
- While on treatment, the average daily prednisone dose is the sum of all prednisone doses over 7 consecutive days, including the day of interest, divided by 7, unless otherwise specified.
- This average dose will be categorised as 0, >0 to ≤7.5, >7.5 to ≤40, and >40 mg/day. The
 average daily prednisone dose will be calculated for weeks 24 and 48 for each year.

Prednisone Equivalent Daily Dose Conversions

- At data base lock, all preferred terms identified with an ATC code beginning with 'H02' will be
 reviewed to ensure a conversion factor exists for all terms with a systemic or intra-articular route
 of administration.
- Similarly, all routes of administration for preferred terms
- Reported dose of systemic steroid is converted to prednisone equivalent dose using a conversion factor for each medication (refer to online calculator http://www.globalrph.com/corticocalc.htm).
 - Prednisone equivalent dose (mg/day) =
 Collected dose (mg) x Conversion Factor x Frequency Factor

[figure not shown]
Preferred Term	Conversion Factor for Prednisone-Equivalent Dose (mg)					
BETAMETHASONE	8.333					
BETAMETHASONE DIPROPIONATE	8.333					
BETAMETHASONE SODIUM PHOSPHATE	8.333					
BUDESONIDE	No conversion applied – nasal spray taken by 1 subject in BEL113750					
CELESTONA BIFAS	7.5					
CORTISONE	0.2					
CORTISONE ACETATE	0.2					
DEFLAZACORT	5/6					
DEPO-MEDROL MED LIDOKAIN	1.25					
DEXAMETHASONE	6.667					
DEXAMETHASONE ACETATE	6.667					
DEXAMETHASONE SODIUM PHOSPHATE	6.667					
FLUOCORTOLONE	3					
HYDROCORTISONE	0.25					
HYDROCORTISONE ACETATE	0.25					
HYDROCORTISONE SODIUM SUCCINATE	0.25					
MEPREDNISONE	1.25					

[figure not shown]
METHYLPREDNISOLONE	1.25
METHYLPREDNISOLONE ACETATE	1.25
METHYLPREDNISOLONE SODIUM SUCCINATE	1.25
PARAMETHASONE	2.5
PREDNISOLONE	1
PREDNISOLONE ACETATE	No conversion applied - conjunctival
PREDNISOLONE SODIUM PHOSPHATE	1

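### SAP 7.1.3 ties the yearly maximum steroid dose to Week 24 and Week 48 values and never defines the maximum; read literally, it would miss most short steroid pulses

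*SAP*

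**What the plan says.** SAP 7.1.3 describes the display in two sentences. The first is "Prednisone equivalent corticosteroid daily dose will be mapped to belimumab visits occurring at Year 1 Day 0, as well as weeks 24 and 48" of each year, with the definitions left to Appendix 5. The second is "Maximum prednisone equivalent corticosteroid daily dose will be summarised within the year intervals". Five classes follow: none, above 0 to 7.5, above 7.5 to 40, above 40 mg, and unknown. No rule says when the unknown class applies.

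Appendix 5 (11.5.3) contains two relevant items. One is a conversion of each recorded dose to a prednisone-equivalent mg/day. The other is an average daily dose, which on treatment is "the sum of all prednisone doses over 7 consecutive days, including the day of interest, divided by 7". It adds that the "average daily prednisone dose will be calculated for weeks 24 and 48 for each year", with the same four numeric dose classes. It gives no derivation of a maximum.

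Section 7.1.2 says: "Use of prednisone or other corticosteroids during the study were collected as a running log with other concomitant medications". Table 7 in 7.1 lists a display called "Prednisone and Other Corticosteroids by Year Interval" and footnotes it as the maximum-dose category. In Appendix 12, Table 2.3 is SLE medication by year interval and Table 2.4 is shifts in dose by visit. No title there names the maximum.

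**The concern.** Section 7.1.3 concerns only the yearly maximum; shifts in the average dose by visit have their own section, 7.1.4. A programmer who follows the mapping sentence into Appendix 5 finds one visit-level quantity, the 7-day average at Weeks 24 and 48, and would take the larger of about two such averages per year. That is not the highest dose in the year.

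Peak steroid use carries information in this study. Protocol 5.3.1 allows more latitude in background medication than the parent study did. SAP Table 1 dropped duration of SRI response because freer prescribing could confound it. A steroid burst is one sign of lost disease control, and a display that samples steroid dose twice a year would hide most short bursts.

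**Working it through.** The plan gives no capture rate, course length or course frequency, so it has no figure to reproduce. The check is one of coverage.

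Inputs:
- Visit spacing: "Calendar represents a yearly (48-week) ongoing visit schedule until the subject is terminated from the study" (SAP 11.1.1). Weeks 24 and 48 of a 48-week cycle are 168 days apart.
- Averaging window: 7 days ending on the visit day (11.5.3).
- Year interval: "assessments will be slotted into year intervals using a 365-day calendar year" (11.2.1).
- Assumed, not in the documents: course length L, ranged from 1 to 14 days, and a uniformly random start day.

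**Windows per year.** Counted from first dose on a 336-day cycle, the mapped visits fall on days 168, 336, 504, 672 and so on. That puts two in each of the first five 365-day intervals and three in the sixth (days 1848, 2016 and 2184). Two windows cover 14 of 365 days, or 3.8%.

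**Chance that a course touches no window.** Within a 168-day gap, P(missed) = 1 − (7 + L − 1)/168.

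| L (days) | Calculation | Missed |
|---|---|---|
| 1 | 1 − 7/168 | 95.8% |
| 3 | 1 − 9/168 | 94.6% |
| 5 | 1 − 11/168 | 93.5% |
| 7 | 1 − 13/168 | 92.3% |
| 14 | 1 − 20/168 | 88.1% |

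A second route uses two windows in a 365-day year: P(touched) = 2(7 + L − 1)/(365 − L + 1). For L = 3 this is 18/363 = 5.0%, so 95.0% are missed. For L = 14 it is 40/352 = 11.4%, so 88.6% are missed. The two routes agree closely.

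If the mapped value were the dose on the visit day alone, P(missed) = 1 − L/168: 99.4% for 1 day, 98.2% for 3 days and 91.7% for 14 days. Over lengths of 1 to 14 days and both kinds of window, the range is 88% to 99%.

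Uniform timing is, if anything, favourable to the plan. A course started the day after a visit, because of a flare seen at that visit, falls outside a look-back window.

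**Longer courses.** A 60-day course touches a window with probability 2(7 + 60 − 1)/(365 − 60 + 1) = 132/306 = 43%. Continuous use is always caught.

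**Dilution inside a window.** These doses only illustrate the arithmetic. With 7.5 mg/day as background, 60 mg for 3 days wholly inside a window averages (3 × 60 + 4 × 7.5)/7 = 210/7 = 30 mg/day, below the top class. With 100 mg for 3 days, full overlap gives 330/7 = 47.1, but two days of overlap give 237.5/7 = 33.9. Only 5 of 168 start days therefore reach the top class, and 97.0% do not.

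**Consistency between tables.** Section 7.1.2 summarises corticosteroids by year, and 11.2.1 counts whatever was taken during the interval. A subject given only a between-visit systemic course is a corticosteroid user in Table 2.3. Under the literal reading of 7.1.3 the same subject has 0 mg at both visits and falls in the no-use class for that year.

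**Year 0-1.** At baseline the average covers the 7 days before Day 0 (11.5.3). Letting the Day 0 value feed the first-year maximum would put a pre-belimumab dose into an interval that starts at first treatment (11.2.1).

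**All-days maximum.** If every logged day counts, no course with a computable dose is lost through visit sampling.

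**The case against.** The strongest reply is that the literal reading is inferred. A reader might conclude that the plan certainly loses 95% of short pulses. The documents do not support that. Section 7.1.3 never says that the maximum is limited to the mapped values. Steroids were logged continuously, 11.2.1 reports concomitant medication by what is taken during the interval, and the mg/day conversion in 11.5.3 has no visit or 7-day restriction. The title of 7.1.3 says daily dose and that of 7.1.4 says average daily dose. All of this fits an all-days maximum. What remains is that the mapping sentence would then have no purpose in a section about the maximum, and that the appendix it cites cannot settle the question.

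A reader might also infer that the class above 40 mg/day would be nearly empty. That is too strong: sustained courses are caught, and the documents do not say how much high-dose use is brief.

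Nor is the display shown to be missing from Appendix 12. It may sit inside Table 2.3, and the shells are in a separate document. The list should say which table carries it.

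Finally, between-visit steroid use is visible elsewhere: Table 2.3, Listing 16, the day counts in 8.1.5, and the flare index with its between-visit log (8.1.6). That limits the harm, but none of these reports the yearly peak dose by class.

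**Conclusion.** The point stands as a flaw in the derivation. The only rule that 7.1.3 gives, followed literally, yields the larger of about two 7-day averages and not a yearly maximum; the all-days reading is possible but unstated. Two defensible programs would give materially different tables.

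The size is conditional on three things: the literal reading, the 7-day window and random timing. Then about 95% of 3-day pulses and 88% to 89% of 14-day bursts touch neither window, and some that do are averaged below 40 mg/day. Course lengths, doses and background dose are assumptions. The display is descriptive and not a listed endpoint, so no efficacy or adverse event conclusion depends on it. It should still be corrected, because it would understate what its title promises and could contradict Table 2.3.

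**What to change.** Replace the mapping sentence in SAP 7.1.3 with:

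*The maximum is the highest total prednisone-equivalent dose on any calendar day within the 365-day year interval, from the concomitant medication log. Records whose dose cannot be computed (PRN or unknown frequency, or dates too incomplete to place) are excluded from the daily total. A subject-year whose only steroid records are of this kind is classed Unknown.*

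The second part is needed because 11.5.3 gives PRN and unknown frequencies a null factor and 11.6.2.1 leaves partial dates unimputed. It also gives the unknown class a definition.

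Keep the 7-day averages for Table 2.4 and the other average-dose displays (8.2.11 to 8.2.13). State in Appendix 12 which table carries the maximum-dose display listed in Table 7.

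The cost is SAP wording and minor programming. The log exists, and 8.1.5 already needs a dose for each day. Reported maxima will be higher than under the visit-based reading.
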